2. STUDY OBJECTIVES

The primary objectives of this study are:

- To evaluate the relative bioavailability of a test formulation of lofexidine granules for reconstitution (oral), final concentration 90 µg/mL ([REDACTED] compared to the Orange Book RS/RLD product, LUCEMYRA tablets, EQ 0.18 mg base (US WorldMeds, LLC) under fasted conditions,
and
- To evaluate the effect of food on the relative bioavailability of lofexidine granules for reconstitution (oral) when administered under fed compared to fasted conditions, following a single 0.36 mg dose to healthy adult male and female subjects.

The secondary objective is:

- To assess the safety and tolerability of a single 0.36 mg oral dose of lofexidine granules for reconstitution formulation when administered to healthy subjects under fasted and fed conditions.

3. OVERALL STUDY DESIGN

This is an open-label, single-dose, randomized, three-treatment, three-period, four-sequence, crossover study comparing equal doses of the test formulation and reference product under fasted conditions and comparing the bioavailability of the granules for reconstitution (test formulation) under fed and fasted conditions. In two of the study periods, a single 0.36 mg dose of lofexidine will be administered to subjects following an overnight fast of at least 10 hours. In a third study period, a single 0.36 mg dose of lofexidine will be administered 30 minutes after the start of an

STATISTICAL ANALYSIS PLAN

PROTOCOL No. USWM-LX2-1001 / [REDACTED]

LOFEXIDINE GRANULES FOR RECONSTITUTION (ORAL) FORMULATION, 90 μ G/ML

FDA-recommended standardized high-fat, high-calorie breakfast preceded by an overnight fast of at least 10 hours. The subjects will receive either lofexidine granules for reconstitution (oral)[†] (Treatment A or C) or two (2) LUCEMYRA tablets, EQ 0.18 mg base (Treatment B). The subjects will receive the test formulation in two of the study periods and the reference product in a third study period according to a four-sequence randomization schedule.

[†] The volume of lofexidine granules for reconstitution to be administered to subjects will be included in the Pharmacy Manual, to be provided by the Sponsor prior to study start.

Serial blood samples will be collected at pre-dose and at specified time points over 54 hours after dosing in each study period. Subjects will be confined at the clinical facility from at least 10.5 hours before dosing until after the 54-hour blood sample collection in each study period. The interval between doses will be at least 7 days.

The plasma concentrations of lofexidine will be measured by fully validated analytical procedures. Statistical analysis using an average bioavailability approach will be performed to estimate the bioavailability of the test formulation relative to the reference product under fasted conditions. The bioavailability of the granules for reconstitution (test formulation) under fasted and fed conditions will also be compared.

For evaluation of the safety endpoint, the following assessments will be performed throughout the study: collection of medical history and Adverse Events (AEs), laboratory tests, vital signs, physical examination, 12-lead electrocardiograms (ECGs), and Columbia Suicidality Severity Rating Scale (C-SSRS) assessments. No formal statistical testing will be performed on safety variables.

STATISTICAL ANALYSIS PLAN

PROTOCOL No. USWM-LX2-1001 / [REDACTED]

LOFEXIDINE GRANULES FOR RECONSTITUTION (ORAL) FORMULATION, 90 µG/ML

STUDY SCHEMATIC

Study Phase	Screening	Periods I, II and III				End of Study Day 3 Period III
		Check-In Day -1	Day 1	Day 2	Day 3	
Informed Consent	X					
Social, Medical History and Demographic Data	X					
Physical Examination ¹	X	X			X	X
C-SSRS ²		X			X	X
Virology Testing	X					
FSH testing (if applicable) ³	X					
12 Lead ECG ⁴	X	X	X		X	X
Clinical Lab Tests ⁵	X					X
Inclusion/Exclusion	X					
Eligibility		X				
Vital Signs ⁴	X	X	X		X	X
Drug and Alcohol Screen ⁶	X	X				
Serum Pregnancy Test ⁷	X					X
Urine Pregnancy Test ⁷		X				
Prior and Concomitant Medication	X	X	X	X	X	X
Confinement ⁸		X	X	X	X	
Genotype sampling ⁹			X			
High-fat, high-calorie breakfast ¹⁰			X			
Dosing ¹¹			X			
Taste Assessment ¹²			X			
PK sampling ¹³			X	X	X	
Adverse Events ¹⁴		X	X	X	X	X

1. To be performed as specified in Sections 5.3.1.1 (screening) and 5.5.5 of the Clinical Study Protocol.
2. C-SSRS to be obtained as specified in Section 5.5.5 of the Clinical Study Protocol.
3. To be performed as specified in Appendix 8.1.6 of the Clinical Study Protocol, if applicable.
4. ECGs and vital signs to be measured as specified in Sections 5.3.1.1 and 5.3.3 (screening) and 5.5.5 of the Clinical Study Protocol. Note: ECG to be conducted at check-in for Periods II and III **only**.
5. Clinical laboratory tests (see Appendix 8.1.1 of the Clinical Study Protocol) to be performed as specified in Sections 5.3.1.1 (screening) and 5.5.4 of the Clinical Study Protocol.
6. For all subjects, test results must be negative before drug will be administered to the subject. Alcohol tested at check-in only. Drug and alcohol tests, as appropriate, to be performed as specified in Appendix 8.1.3 of the Clinical Study Protocol (at screening) and Appendix 8.1.4 of the Clinical Study Protocol (at check-in).
7. Female subjects only. For all female subjects, test results must be negative before drug will be administered to the subject. Pregnancy tests to be performed as specified in Appendix 8.1.5 of the Clinical Study Protocol.
8. Subjects should enter the clinical facility at least 10.5 hours before dosing and will remain confined until at least 54 hours after dosing in each study period.
9. Blood sample to be collected in Period I as specified in Appendix 8.1.2 of the Clinical Study Protocol.
10. The standardized high-fat, high-calorie breakfast will be provided as specified in Section 5.4.4 of the Clinical Study Protocol.
11. Single dose to be administered as specified in Section 5.4.1 of the Clinical Study Protocol.
12. Treatments A or C only. To be performed as outlined in Section 5.4.1 and Appendix 8.2 of the Clinical Study Protocol.
13. Blood samples to be collected as specified in Section 5.6 of the Clinical Study Protocol.
14. From dosing in Period I until the end of the study.

STATISTICAL ANALYSIS PLAN

PROTOCOL No. USWM-LX2-1001 / [REDACTED]

LOFEXIDINE GRANULES FOR RECONSTITUTION (ORAL) FORMULATION, 90 µG/ML

4. RANDOMIZATION

Treatments will be administered according to a three-treatment, three-period, four-sequence design as outlined below. The randomization will be generated in blocks of four with each sequence occurring once in each block.

Sequence	Period I	Period II	Period III
1 (N=4)	Treatment B	Treatment A	Treatment C
2 (N=4)	Treatment B	Treatment C	Treatment A
3 (N=4)	Treatment A	Treatment C	Treatment B
4 (N=4)	Treatment C	Treatment A	Treatment B

Treatment A = Lofexidine granules – fasted conditions
Treatment B = LUCEMYRA tablets – fasted conditions
Treatment C = Lofexidine granules – fed conditions

The randomization schedule will be generated by the Biostatistics Department at [REDACTED] before the first dosing period using SAS®, Version 9.4 or higher.

5. SAMPLE SIZE

A sample size of 16 subjects enrolled to complete 12 subjects is considered, by the Sponsor, sufficient to meet the objectives of this study. The sample size for this study was determined based on clinical and practical considerations and not on a formal statistical power calculation.

6. ANALYSIS POPULATIONS

6.1 Pharmacokinetic Population

Data from subjects who have sufficient plasma concentrations to characterize C_{max} and AUC_{0-t} of at least one of the study treatments (A, B or C) will be included in the pharmacokinetic analysis. Data from any subject/period that does not provide sufficient plasma concentrations to characterize C_{max} and AUC_{0-t} will be excluded from the pharmacokinetic analysis.

Data from subjects who have sufficient plasma concentrations to characterize C_{max} and AUC_{0-t} from at least two periods of the study, one of which includes Treatment A, will be included in the comparative statistical analysis.

6.2 Safety Population

The safety population will include all subjects who are administered at least one dose of a study treatment (A, B or C).

7. STATISTICAL ANALYSIS METHODS

Data will be summarized with respect to demographic, baseline characteristics, safety, and pharmacokinetic (PK) variables.

For categorical variables, the number and percent of each category within a parameter will be calculated for non-missing data. For continuous variables, statistics will include number of observations, mean, standard deviation, median, minimum, and maximum values.

7.1 Baseline Characteristics

7.1.1 Baseline Demographics

Demographic information collected at screening includes age, sex, ethnicity, race, body weight (lbs), height (in), BMI, and tobacco use. Body weight and height will be converted into kg and cm, respectively, for presentation in listings and tables.

All data will be listed by subject. A summary table will be presented for the safety population.

7.1.2 Medical History

Only clinically significant medical history data, if they exist, will be presented and listed by subject.

7.2 Pharmacokinetic and Statistical Analyses

Pharmacokinetic and statistical services will be performed by [REDACTED]
[REDACTED]. SAS[®], Version 9.4 or higher will be used for all pharmacokinetic and statistical calculations.

No concentration estimates will be provided for missing sample values. Any sample with a missing value will be treated as if the sample had not been scheduled for collection. Data from subjects with missing concentration values (such as missing blood draws, lost samples, samples unable to be quantified) may be used if pharmacokinetic parameters can be estimated using the remaining data points, otherwise data from these subjects will be excluded from the final analysis.

Descriptive statistics (n, mean, SD, % coefficient of variation [%CV], minimum, median, maximum, geometric mean, geometric CV) will be reported for lofexidine concentrations at each time point by treatment.

Linear and semi-logarithmic graphs of the concentration-time profiles for each subject will be provided, using the actual times of sample collections. Graphical presentations of mean results will use the scheduled times of sample collections. Actual sample collection time will be used for calculating the pharmacokinetic parameters, although data will be summarized referencing the scheduled sample collection times.

7.2.1 Pharmacokinetic Parameters

The pharmacokinetic parameters will be determined from the plasma concentration data using a non-compartmental model.

For the test and reference products, the peak exposure (C_{max}) will be the observed maximum plasma concentration; the time to peak exposure (T_{max}) will be the collection time at which C_{max} is first observed.

Areas under the plasma concentration-time curve from time zero to the time of last measurable concentration (AUC_{0-t}) will be calculated by the linear trapezoidal method. Area under the plasma concentration-time curve from time zero to time infinity ($AUC_{0-\infty}$) will be calculated as follows:

$AUC_{0-\infty} = AUC_{0-t} + C_t/\lambda_z$, where C_t is the last measurable plasma concentration and λ_z is the

apparent first-order terminal rate constant.

λ_z will be estimated, when possible, from the negative of the slope of the dataset with the best-fit least-squares linear regression analysis of the terminal ln-linear concentration-time data. The number of data points (3 or more) in the terminal phase (not including C_{max}) to be included in the final regression analysis for an evaluable λ_z will be determined from the dataset that has the highest adjusted R^2 value of 0.7 or more.

λ_z will be considered non-evaluable if (1) the last three terminal points are used to determine λ_z and either the middle or the last point is higher than the preceding point or (2) the resulting adjusted R^2 value is less than 0.7. An evaluable λ_z will be considered not reliable and not reportable if the resulting apparent first-order terminal half-life ($T_{1/2}$) value is longer than the time interval over which λ_z is estimated. If the resulting $T_{1/2}$ value is longer than the time interval over which λ_z is determined, an interval that is longer than the estimated $T_{1/2}$ will be explored. The interval with the next highest adjusted R^2 value will be chosen and the decrease in the adjusted R^2 value will be assessed to determine if a reliable estimation of the λ_z is possible. If λ_z is deemed not reliable then no $T_{1/2}$ and $AUC_{0-\infty}$ values will be reported for that dataset. $T_{1/2}$ will be calculated as $\ln(2)/\lambda_z$.

Apparent volume of distribution during the terminal phase (V_z/F) of the drug from plasma will be calculated as follows: Dose / [$AUC_{0-\infty} \cdot \lambda_z$]).

Apparent total clearance of the drug from plasma (CL/F) will be calculated as follows: Dose / $AUC_{0-\infty}$.

Descriptive statistics (n, mean, SD, % coefficient of variation (%CV), geometric mean, minimum, median, maximum) will be reported for all PK parameters.

7.2.2 Statistical Analyses

A linear mixed effect model with treatment, sequence and period as fixed effects and random effects of subject nested within sequence will be used. Sequence effects will be tested against the Type III mean square term for subject-within sequence at the two-sided $\alpha = 10\%$ level of significance. Least squares means for the treatments (LSMEANS statement), the differences between adjusted treatment means, and the standard errors associated with these differences (ESTIMATE statement) will be estimated.

Two-sided confidence intervals (90%) on the geometric mean ratios (obtained from logarithmic transformed data) for AUC_{0-t} , $AUC_{0-\infty}$ and C_{max} for the comparison of Treatment A to Treatment B (to compare the test formulation and reference product under fasted conditions) and the comparison of Treatment C to Treatment A (to compare the granules for reconstitution [test formulation] under fed and fasted conditions) will be constructed to test two one-sided hypotheses at the $\alpha = 0.05$ level of significance.

The statistical model will be conducted separately for Treatment A versus Treatment B analysis and for Treatment C versus Treatment A analysis using an incomplete block design.

7.3 Safety Analysis

No formal statistical testing will be performed on safety variables.

7.3.1 Adverse Events

Adverse events (AEs) and Serious Adverse Events (SAEs) will be collected through both solicited and unsolicited means from dosing in Period I until the end of the study.

All reported AEs will be coded and classified according to the MedDRA Version 23.0 or higher adverse event dictionary. Each adverse event is to be evaluated for date of start and end, seriousness, severity, causal relationship to study treatment, action taken and outcome. The severity is characterized as mild, moderate or severe. The relationship to the study treatment is characterized as unrelated or related.

Adverse events will be listed by subject, treatment, system organ class, and preferred term. The incidence of AEs will be summarized by system organ class (SOC), preferred term (PT) and treatment. Subjects will be counted once per preferred term and once per system organ class, per treatment. The system organ classes will be ordered by decreasing total frequency then alphabetically. The preferred terms within each system organ class will be ordered by decreasing total frequency then alphabetically.

The summary table for Adverse Events will be based upon the safety population. AEs and SAEs will be summarized by overall number of AEs in the final report text, per treatment. The number of AEs leading to withdrawal from the study or SAEs will also be summarized in text.

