5.5.1.1 Definitions

Adverse Event

Per 21 Code of Federal Regulations (CFR) 312.32, an AE is any untoward medical occurrence associated with the use of a drug in humans, whether or not considered drug related. Therefore, such an occurrence is considered an AE if it occurs after the Investigational Medicinal Product (IMP) has been administered. An AE includes any noxious, pathologic, or unintended change in anatomic, physiologic, or metabolic functions as indicated by physical signs, symptoms and/or laboratory changes.

CONFIDENTIAL PROTOCOL

A study to evaluate the relative bioavailability of a test formulation of lofexidine granules for reconstitution and the effect of food on the bioavailability of the test formulation in healthy adult subjects

[REDACTED]. Study events occurring after signing informed consent but prior to IMP administration are to be documented in the subject's medical history source and eCRF.

Serious Adverse Event

Per 21CFR.312.32, an SAE is an AE occurring after administration of the IMP at any dose, comparator or placebo, that fulfils one or more of the following:

1. Results in death during the period of protocol-defined surveillance
2. Is life-threatening (*NOTE: The term "life-threatening" in the definition of "serious" refers to an event in which the subject, in the view of the Investigator, was at immediate risk of death at the time of the event; it does not refer to an event which hypothetically might have caused death if it were more severe*)
3. Requires inpatient hospitalization or prolongation of existing hospitalization
4. Results in persistent or significant disability or incapacity or substantial disruption of the ability to conduct normal life functions
5. Results in a congenital anomaly/birth defect
6. Is an important medical event

Hospitalization: Outpatient treatment in an emergency room is not in itself an SAE, although the reasons for it might be (e.g., bronchospasms, laryngeal edema). Hospital admission and/or surgical operations planned before or during a study are not considered SAEs if the illness or disease existed before the subject was enrolled in the study, provided that it did not deteriorate in an unexpected way during the study. It should be noted that for this study, subjects with planned or anticipated surgery will not be enrolled into the study.

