5.5.4 Clinical Laboratory Evaluations

All subjects will be screened for alcohol, and marijuana (THC), cocaine, benzodiazepine, and opiate metabolites using immediate saliva/urine testing

CONFIDENTIAL PROTOCOL

A study to evaluate the relative bioavailability of a test formulation of lofexidine granules for reconstitution and the effect of food on the bioavailability of the test formulation in healthy adult subjects

at check-in each study period (see [Appendix 8.1.4](#)). Subjects with positive results will be withdrawn from the study.

All female subjects will have a urine pregnancy test performed at check-in each study period (see [Appendix 8.1.5](#)). Subjects with positive results will be withdrawn from the study.

A 12.5 mL sample of blood will be collected after the last pharmacokinetic blood sample in Period III (or early termination) for a post-study hematology and clinical chemistry determination and a urine sample for urinalysis (see [Appendix 8.1.1](#)). Subjects will be instructed to not donate blood or plasma until at least 30 days after the last dose of study medication.

In Period I, a blood sample for genotyping to determine CYP2D6 genotype/lofexidine metabolizer status will be obtained at the time of the pre-dose (Day 1, 0-hour) pharmacokinetic sample (see [Appendix 8.1.2](#)). This sample will only be analyzed, if needed, upon review of the PK results, as determined by the Sponsor.

All female subjects will have a serum pregnancy test performed at the end of the study (or early termination) (see [Appendix 8.1.5](#)).

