5.7.2 Safety Analysis

For safety, all AEs, ECGs, VS and safety laboratory values will be listed for each subject and tabulated by treatment. Physical examination data will also be listed.

Safety (12-lead) ECG changes from baseline will be presented in a shift table (i.e., normal to abnormal) at each post-dose time point. For vital signs, descriptive statistics will be used to summarize the observed values at each time point and the change from baseline at each post-dose time point.

No formal statistical testing will be performed on safety variables.

CONFIDENTIAL PROTOCOL

A study to evaluate the relative bioavailability of a test formulation of lofexidine granules for reconstitution and the effect of food on the bioavailability of the test formulation in healthy adult subjects

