7.3.6 Clinical Laboratory Tests

All subjects will have chemistry, hematology, and urinalysis performed at screening and end of study.

Clinical laboratory results will be listed by subject and any clinically significant out of range laboratory results will be flagged.

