Preferred Term	x (xx.x%)	x (xx.x%)	x (xx.x%)	x (xx.x%)
...				

n = Number of subjects reporting AE

% = (Number of subjects reporting AE / number of subjects dosed with respective study drug) x 100

Subjects counted once per preferred term and once per system organ class, per treatment.

Treatment A = ## subjects dosed.

Treatment B = ## subjects dosed.

Treatment C = ## subjects dosed.

Created on: DDMMYYYY

Page 1 of N

Programming Note 1: Subjects with more than one PT for the same SOC will be counted only once. Subjects with more than one incidence of same PT will be counted only once.

Programming Note 2: The system organ classes will be ordered by decreasing overall frequency then alphabetically. The preferred terms within each system organ class will be ordered by decreasing overall frequency then alphabetically

STATISTICAL ANALYSIS PLAN

PROTOCOL No. USWM-LX2-1001 / [REDACTED]

LOFEXIDINE GRANULES FOR RECONSTITUTION (ORAL) FORMULATION, 90 µG/ML

Table 12.5.1 Summary of Vital Signs

Evaluation	Treatment	Time Point	Observed Data				Change from Baseline			
			n	Mean (SD)	Median	Min, Max	n	Mean (SD)	Median	Min, Max
Diastolic Blood Pressure (mmHg)	A	Pre-dose (Baseline)	xx	xx.x (xx.x)	xx.x	xx.x, xx.x	xx	xx.x (xx.x)	xx.x	xx.x, xx.x
		3.5 hr	xx	xx.x (xx.x)	xx.x	xx.x, xx.x				
		7.5 hr	xx	xx.x (xx.x)	xx.x	xx.x, xx.x				
	B	etc.	xx	xx.x (xx.x)	xx.x	xx.x, xx.x	xx	xx.x (xx.x)	xx.x	xx.x, xx.x
		Pre-dose (Baseline)								
		3.5 hr								
		7.5 hr								
		etc.								
	C	Pre-dose (Baseline)	xx	xx.x (xx.x)	xx.x	xx.x, xx.x	xx	xx.x (xx.x)	xx.x	xx.x, xx.x
		3.5 hr								
		7.5 hr								
		etc.								
Pulse (beats/min)	A	Pre-dose (Baseline)	xx	xx.x (xx.x)	xx.x	xx.x, xx.x	xx	xx.x (xx.x)	xx.x	xx.x, xx.x
		3.5 hr	xx	xx.x (xx.x)	xx.x	xx.x, xx.x				
		7.5 hr	xx	xx.x (xx.x)	xx.x	xx.x, xx.x				
	A	etc.	xx	xx.x (xx.x)	xx.x	xx.x, xx.x	xx	xx.x (xx.x)	xx.x	xx.x, xx.x

Created on: DDMMYYYY

Page 1 of N

Programming Note: If any pre-dose assessment data are missing, the nearest non-missing pre-dose value will be used as the baseline.

STATISTICAL ANALYSIS PLAN

PROTOCOL No. USWM-LX2-1001 / [REDACTED]

LOFEXIDINE GRANULES FOR RECONSTITUTION (ORAL) FORMULATION, 90 µG/ML

Table 12.5.2 Shift Table for Changes from Baseline in ECGs

Treatment	Pre-dose (Baseline)	3.5 Hours Post-dose			Release	
		Normal n (%)	Abnormal (NCS) n (%)	Abnormal (CS) n (%)	Normal n (%)	Abnormal (NCS) n (%)
A	Normal	xx (xx.x)	xx (xx.x)	xx (xx.x)	xx (xx.x)	xx (xx.x)

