xxxx	A	Neither like nor dislike							
xxxx	C	Dislike slightly							
xxxx	C	Dislike moderately							
xxxx	C	Dislike very much							
...									

*Taste Assessment Questionnaire completed once by each subject, only after the subject's first dose of lofexidine granules (Treatment A or C).

Created on: DDMMYY YYYY

Page 1 of N

STATISTICAL ANALYSIS PLAN

PROTOCOL No. USWM-LX2-1001 / [REDACTED]

LOFEXIDINE GRANULES FOR RECONSTITUTION (ORAL) FORMULATION, 90 µG/ML

Listing 16.2.7 Adverse Events

Subject No.	System Organ Class/ MedDRA Preferred Term/ AE Term	Treatment	Onset Date Time	Onset Date Time	Severity	Relationship	Outcome	Action Taken with Study Treatment	Other Action Taken	SAE
xxxx	Nervous system disorders / Headache / Headache	A	dd/Mmm/yyyy hh:mm	dd/Mmm/yyyy hh:mm	Mild	Unrelated	Recovered/ Resolved	Dose Not Changed	None	No
xxxx	Investigations / Blood pressure increased / Blood pressure increased	C	dd/Mmm/yyyy hh:mm	dd/Mmm/yyyy hh:mm	Moderate	Related	Recovered/ Resolved	Dose Not Changed	None	No
...										

Created on: DDMMYYYY

Page 1 of N

STATISTICAL ANALYSIS PLAN

PROTOCOL No. USWM-LX2-1001 / [REDACTED]

LOFEXIDINE GRANULES FOR RECONSTITUTION (ORAL) FORMULATION, 90 µG/ML

Listing 16.2.8.1 Serum Chemistry Laboratory Test Results

Subject No.	Visit	Date	Time	Test	Result	Units	Clinically Significant (if out of range)
xxxx	Screening	dd/Mmm/yyyy	hh:mm	Alanine Aminotransferase	xx.x	U/L	
xxxx	Screening	dd/Mmm/yyyy	hh:mm	Alkaline Phosphatase	xx.x	U/L	
xxxx	Screening	dd/Mmm/yyyy	hh:mm	Aspartate Aminotransferase	xx.x	U/L	
xxxx	Screening	dd/Mmm/yyyy	hh:mm	Bilirubin	xx.x	mg/dL	
xxxx	Screening	dd/Mmm/yyyy	hh:mm	Creatinine	xx.x	mg/dL	
xxxx	Screening	dd/Mmm/yyyy	hh:mm	Glucose	xx.x	mg/dL	
xxxx	Screening	dd/Mmm/yyyy	hh:mm	Potassium	xx.x	mmol/L	
xxxx	Screening	dd/Mmm/yyyy	hh:mm	Urea Nitrogen	xx.x	mg/dL	
xxxx	Screening	dd/Mmm/yyyy	hh:mm	Magnesium	xx.x	mg/dL	
xxxx	Screening	dd/Mmm/yyyy	hh:mm	Sodium	xx.x	mEq/L	
xxxx	Screening	dd/Mmm/yyyy	hh:mm	Chloride	xx.x	mEq/L	
xxxx	End of Study/ Early Termination	dd/Mmm/yyyy	hh:mm	Alanine Aminotransferase	xx.x	U/L	
...				

Created on: DDMMYY

Page 1 of N

Note: Similar listings will be produced for hematology and urinalysis.

Listing 16.2.8.2 Hematology Laboratory Test Results**Listing 16.2.8.3 Urinalysis Laboratory Test Results**

STATISTICAL ANALYSIS PLAN

PROTOCOL No. USWM-LX2-1001 / [REDACTED]

LOFEXIDINE GRANULES FOR RECONSTITUTION (ORAL) FORMULATION, 90 µG/ML

Listing 16.2.8.4 Vital Signs

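### Does one laboratory sample taken after all three treatments undermine the by-treatment safety tables?

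*SAP*

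**What the plan says.** Protocol 5.7.2 states that "all AEs, ECGs, VS and safety laboratory values will be listed for each subject and tabulated by treatment". The laboratory schedule is thin: SAP 7.3.6 says "All subjects will have chemistry, hematology, and urinalysis performed at screening and end of study", and Protocol 5.5.4 places the second of these after the last dose: "A 12.5 mL sample of blood will be collected after the last pharmacokinetic blood sample in Period III (or early termination").

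For output, SAP 7.3.6 plans only this: "Clinical laboratory results will be listed by subject and any clinically significant out of range laboratory results will be flagged". The shells in SAP section 9 agree. "Listing 16.2.8.1 Serum Chemistry Laboratory Test Results" and its hematology and urinalysis counterparts are organised by subject and visit, have no treatment column, and are not accompanied by a laboratory summary table. Adverse events, vital signs and ECGs do have by-treatment shells.

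Protocol 5.5.1.1 counts as an adverse event a change "as indicated by physical signs, symptoms and/or laboratory changes", so an abnormal end-of-study result can become one. SAP 7.3.1 then requires a treatment for it: "The incidence of AEs will be summarized by system organ class (SOC), preferred term (PT) and treatment". The percentage in Table 12.2.2.1 is "Number of subjects reporting AE / number of subjects dosed with respective study drug) x 100". The visible text does not say how an event is assigned to a treatment. The SAP's front pages and the Note to File of 08 Feb 2021 cited in SAP section 1 were not available to check.

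**The concern.** Two things look wrong. First, the protocol promises a by-treatment laboratory table that its own schedule cannot make informative, and the SAP drops that table without saying so. Two current documents therefore describe different outputs.

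Second, the difficulty seems to carry over into the adverse event table. An event first detected on the final sample could have arisen after any of the three doses, but it must be shown under one. A programmer left to choose might use the last dose. The last dose is not balanced across treatments, because the reference tablets are given in Period III in two of the four sequences. The tablets would then collect more of these events than either granules arm for no pharmacological reason, and the granules would look comparatively safer. Safety of the granules is the secondary objective, so an artifact in their favour deserves a check.

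**Working it through.** **1. Is there really only one post-dose laboratory draw?** The blood volumes confirm it. Pharmacokinetic sampling is 3 periods × 17 samples × 6 mL = 306 mL, as the protocol states. Adding 17 mL for virology and 12.5 mL for laboratory tests at screening (Protocol 5.3.1.1), and 12.5 mL at end of study (Protocol 5.5.4), gives 306 + 17 + 12.5 + 12.5 = 348 mL, within the stated 352.5 mL for men. A draw after every period would need 306 + 17 + 12.5 + 3 × 12.5 = 373 mL, which does not fit. The single draw is the design. Unscheduled evaluations are allowed, but they are not a planned source of data for a table.

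**2. Last dose by treatment.** The sequences in SAP section 4 are BAC, BCA, ACB and CAB, with 4 subjects each. Period III is therefore C in 4, A in 4 and B in 8. With all 16 completing, each treatment has 16 subjects dosed.

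**3. Size of the artifact under a last-dose rule.** Suppose every subject has the same risk r of an event first found on the final sample. Expected incidence is r × 8/16 for B and r × 4/16 for A and for C. The B:A ratio is 2.0 whatever r is, and A and C are equal. The documents give no value for r, so a range is assumed:

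| Assumed r | B incidence (subjects) | A or C incidence (subjects, each) |
|---|---|---|
| 2% | 1.0% (0.16) | 0.5% (0.08) |
| 5% | 2.5% (0.4) | 1.25% (0.2) |
| 10% | 5.0% (0.8) | 2.5% (0.4) |
| 20% | 10.0% (1.6) | 5.0% (0.8) |

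**4. With the planned 12 completers** (same r for all; the four dropouts stop after Period I or II):

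- One subject per sequence stops after Period I: last dose B 8, A 4, C 4; dosed B 14, A 13, C 13. Ratio (8/14)/(4/13) = 1.86.
- One per sequence stops after Period II: last dose B 6, A 5, C 5; dosed B 14, A 15, C 15. Ratio (6/14)/(5/15) = 1.29.
- Lowest B:A ratio: all four CAB subjects stop after Period II. (4/12)/(8/16) = 0.67.
- Highest finite B:A ratio: one BAC and three BCA subjects stop after Period I. (12/16)/(1/12) = 9.0.
- Five patterns leave no last dose of A and five leave none of C, so the ratio of B to that arm has no upper bound. An example is all four BCA subjects stopping after Period II, with last doses A 0, B 8, C 8.

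**5. Is assigning events to the most recent dose neutral for the rest?** No. At the minimum 7-day (168 h) interval, with 54 h of follow-up after the Period III dose, A and C are each followed by another dose in 12 subjects and are last in 4: 12 × 168 + 4 × 54 = 2,232 h. B is followed by another dose in 8 and is last in 8: 8 × 168 + 8 × 54 = 1,776 h. The ratio is 1,776/2,232 = 0.80, with 16 dosed in each arm. For ordinary events the same sequence table therefore gives B less follow-up, the opposite direction to step 3.

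**The case for a change.** The best argument for acting is that it is cheap and timely. One sentence in SAP 7.3.6 would record the laboratory departure. A rule in SAP 7.3.1, set before database lock, would take the choice away from the programmer. The artifact also runs the convenient way, against the reference, in a study with granules safety as an objective. One could go further and count laboratory-found events from subjects given more than one treatment only in the Overall column.

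The facts behind this stand: the two documents differ on laboratory output, and no assignment rule is visible. The inference to a needed change does not. The laboratory sentence would alter no output, since the SAP already presents the data in the form the schedule supports. The Overall-only rule has a real cost. A laboratory event found about 54 h after a Period III granules dose would disappear from the granules columns, which are the ones the secondary objective concerns. It would also leave unsettled what the treatment entry in Listing 16.2.7 and the per-treatment counts in the report text should show. And it would sit beside a most-recent-dose rule for all other events that carries the unequal follow-up in step 5.

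**Conclusion.** No change to the plan follows. On the laboratory side, a table by treatment would be uninformative in completers, and the SAP replaces it with listings by subject and visit. The unrecorded departure is a documentation slip with no effect on any result.

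On the adverse event side, this is a gap that analysts fill sensibly. The 2.0 ratio holds only if a last-dose rule is applied, all 16 subjects complete, and such events occur. At assumed risks of 2% to 20%, the expected excess on B over either granules arm is 0.08 to 0.8 of a subject. Uneven dropout can move the ratio a long way in either direction, but always on the same handful of events. The comparison affected is tablets against granules, whereas the secondary objective is the safety of the granules fasted and fed; A and C stay equal in expectation when all complete. SAP 7.3 rules out formal testing of safety variables, Listings 16.2.5.1 and 16.2.7 let a reader trace each event to the dosing history, and the pharmacokinetic conclusions are untouched. None of the rules considered gives a clean attribution of a finding made after three treatments, so choosing among them is a trade-off with no clear gain.
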